2.3 Study Endpoints

The study endpoints are listed below, with greater detail concerning these endpoints provided in [Sections 2.3.2 to 2.3.8](#).

Primary Efficacy Endpoint

The primary efficacy endpoint is the WI-NRS 4-point responder rate at Week 10.

Secondary Efficacy Endpoints

The key secondary efficacy endpoints are as follows:

- WI-NRS 4-point responder rate at Weeks 2, 4, 6, and 8
- WI-NRS 3-point responder rate at Weeks 2, 4, 6, 8, and 10
- Change from baseline in WI-NRS at Weeks 2, 4, 6, 8, and 10
- Change from baseline in daily WI-NRS scores through Week 2
- Change from baseline in WI-VAS at Weeks 2, 4, 6, and 10

Safety Endpoints

Safety endpoints include the following:

- Incidence of TEAEs and SAEs
- Changes from baseline in clinical laboratory parameters following study drug exposure
- Changes from baseline in vital sign and ECG parameters following study drug exposure
- Plasma concentrations of serlopitant and metabolites

Exploratory Endpoints

The exploratory endpoints include the following:

- Change from baseline in the Epworth Sleepiness Scale (ESS) to Weeks 2, 4, 6, and 10
- Change from baseline in Static Patient Global Assessment of Itch Severity (sPGA) to Weeks 2, 4, 6, and 10
- Patient Global Impression of Change in Itch Severity (PGIC) at Weeks 2, 4, 6, and 10

2.3.1 *Endpoint Data Capture*

The study endpoints will be captured within the eDC system, from central laboratories, within the IRT system, or a subject eDiary (see [Table 2](#)). The eDiary will be used to capture the WI-NRS data daily. From these measures the primary endpoint will be created. This system will also calculate and provide two measures to the study sites that are required for eligibility determinations: eDiary compliance and baseline 1-week average WI-NRS score.

Table 2 Data Capture Systems

Examination	eDC	Central Laboratory	IRT system	eDiary
Demographics	X			
Paper WI-NRS	X			
Daily WI-NRS				X
WI-VAS / ESS / sPGA	X			
PGIC	X			
ECG	X	X		
Vital signs	X			
Medical history / prior medications	X			
Physical exam	X			
Concomitant medications	X			
Laboratory Results		X		
Urine pregnancy test	X			
PK blood draw		X		
Dispense / collect study drug	X			
AEs/SAEs	X			
Randomization			X	

2.3.2 *Worst Itch - Numeric Rating Scale*

The Itch NRS is a validated, self-reported, instrument for measurement of itch intensity. It uses a 24-hour recall period and asks subjects to rate the worst intensity of their itch on an 11-point scale ranging from 0 (no itch) to 10 (worst itch imaginable). Higher scores indicate greater itch intensity during that 24 period. During the study, WI-NRS assessments will be reported by the subject via eDiary. The daily NRS results will be summarized. The daily results will be averaged to create weekly measures outlined in [Section 2.4](#). A 4-point responder is a subject who had at least a 4-point reduction in score between the week and baseline. A 3-point responder is similarly defined. The intercurrent rules outlined in [Section 2.6](#) will be applied to the responder rate endpoints.

A ‘paper WI-NRS’ will be captured at screening to be used as part of the eligibility criteria. This measure will not be used within the efficacy calculations.

2.3.3 *Worst Itch - Visual Analog Scale*

The Itch VAS is a validated, self-reported, instrument for measurement of itch intensity. It uses a 24-hour recall period and asks subjects to rate the worst intensity of their itch on a 100-mm horizontal line ranging from 0 mm (no itch) to 100 mm (worst itch imaginable). Higher scores indicate greater itch intensity. The VAS measurement will be summarized in centimeters. WI-VAS assessments will be reported by the subject via a paper form administered at study visits.

2.3.4 *Epworth Sleepiness Scale*

The ESS is a quality of life instrument intended to measure daytime sleepiness by use of a very short questionnaire (8 items each scored from 0-3). Each of the eight items have four possible responses: no chance of dozing (0), slight chance of dozing (1), moderate chance of dozing (2), high chance of dozing (3). The ESS total score is the sum of the responses to each item and can range from 0 to 24. If an individual item is missing, the total score will be missing. Higher scores indicate greater daytime sleepiness.

The total score can be interpreted as follows
(<http://epworthsleepinessscale.com/about-the-ess/>):

- 0-10: Normal Daytime Sleepiness
- 11-12: Mild Excessive Daytime Sleepiness
- 13-15: Moderate Excessive Daytime Sleepiness
- 16-24: Severe Excessive Daytime Sleepiness

2.3.5 *Static Patient Global Assessment of Itch Severity*

The Static Patient Global Assessment of Itch Severity (sPGA) is designed to assess overall itch severity. Each subject is asked to rate the severity of his/her itchiness in the past 7 days on a 5-point scale as none, mild, moderate, severe, and very severe. Higher scores indicate greater itch severity.

2.3.6 *Patient Global Impression of Change in Itch Severity*

The Patient Global Impression of Change in Itch Severity (PGIC) is a single item used to assess the change in overall itch severity since the baseline visit. Each subject will rate the change in his/her itch severity on a 7-point scale from (very much better) to (very much worse).

2.3.7 *Safety Parameters*

The following safety parameters are captured within this study.

2.3.7.1 Adverse Events and Serious Adverse Events

The following is a brief summary of terms associated with adverse events. Greater details concerning these terms can be found in the protocol.

An AE is any untoward medical occurrence associated with the use of a drug in humans, whether or not it is considered drug related. An AE is considered treatment emergent, TEAE, if it began on the day of first treatment or after. For AEs that occur on the first day of dosing, the AE will be considered TEAE if the study site indicates that the event occurred after the first study drug dosing. An AE is considered “serious” if it results in death, is a life-threatening AE, results in hospitalization or prolongation of hospitalization, persistent or significant incapacity or substantial disruption of the ability to conduct normal life functions, a congenital anomaly/ birth defect or is an important medical event.

AEs and SAEs will be recorded from the first study drug administration through the end of the follow-up period. After informed consent but prior to initiation of study drug, only SAEs considered by the investigator to be caused by a protocol-mandated intervention will be collected.

AEs will be graded for severity using the National Cancer Institute Common Terminology Criteria for Adverse Events (NCI CTCAE) v5.0 to describe the maximum intensity of the adverse event. As such, severity will be reported as Mild, Moderate, Severe, Very Severe, Life Threatening or Disabling, Death Related.

An investigator’s causality assessment is the determination of whether there exists a reasonable possibility that the investigational product caused or contributed to an AE. Causality of an AE will be assessed by the investigator using the following terms: Likely Related and Likely Unrelated.

Adverse events and medical history will be coded using MedDRA version 21.0.

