- Any medications that, in the investigator's and/or medical monitor's opinion, are suspected of having a causal or contributory role in the subject's pruritus.
- Biologic therapies (other than therapies such as insulins, vaccines)
- Strong CYP3A4 inhibitors (See [Appendix B](#))
- Use of an indoor tanning facility, or natural sun exposure resulting in significant tanning or sunburn
- Any investigational therapy

The following therapies and activities are excluded from 3 weeks prior to randomization through the treatment period. Use is discouraged, though permitted, in the follow-up period:

- Topical therapies or emollients with anti-pruritic properties (including but not limited to anti-histamines, menthol or menthol derivatives, polidocanol, camphor, pramoxine, cannabinoids, colloidal oatmeal baths, and capsaicin)
- Systemic therapies with recognized anti-pruritic properties (including but not limited to H1 antihistamines, doxepin, gabapentin, pregabalin, cannabinoids, kappa-opioid receptor agonists, and mu-opioid receptor antagonists)

Use of any excluded therapies (including those for the treatment of pruritus, or as rescue therapy) should be reported as soon as possible, and will be recorded as protocol deviations for subjects who receive them.

5.7.3 *Rescue Therapies*

The initiation of non-study drug therapy to treat worsening of pruritus is strongly discouraged throughout the treatment period. However, should rescue therapy be required for the safety and well-being of the subject, such use will be recorded and analyzed (see [Section 8.2](#)). The subject may remain on study drug, unless the rescue therapy is an NK₁ receptor antagonist, a systemic biologic therapy, a strong CYP3A4 inhibitor, an investigational therapy, or any therapy that may jeopardize the subject's safety if study drug is continued, in the investigator's and/or Sponsor's opinion.

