8.2 Handling of Missing Data

Should a determination of treatment period (on treatment, pre-treatment, follow-up) be required for adverse events or concomitant medication but the corresponding date is missing, or is a partial date, the event/medication will be considered on treatment unless the portions of the date that are available indicate this is not possible.

If a subject fails to complete their eDiary for a week or more, the WI-NRS endpoints, including the primary endpoint, may be missing. In this case, the WI-NRS change from baseline value will be imputed. The approach uses the subject's last week with data. From that point forward their trajectory will be imputed based upon the trajectory of their treatment group.

The imputation approach first determines the average change for each week for each treatment group. The difference in the weekly measures between weeks n-1 and n will be considered the change for Week n. Any missing changes will be imputed to produce and them combined with the prior known value to produce a change from baseline result. For

example, a placebo subject with known results at Week 4 but missing at Week 6 will have their Week 6 WI-NRS change from baseline imputed as $\Delta_4 + \Delta_{P(4-6)}$, where Δ_4 is the observed change from baseline result for the subject up to Week 4 and $\Delta_{P(4-6)}$ is the average placebo change from Week 4 to 6 (i.e. the average placebo decrease from Week 4 to 6).

For the responder endpoints, the same imputation will be performed and the responder status determined based upon the change from baseline and the subject's disposition and rescue medication status (See [Section 8.8](#)).

As a sensitivity analysis, a similar approach will be used where the imputation step uses multiple imputation methodology.

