1.6 Decision Rule and Sample Size

The significance level for this study is 5% (one-sided). If the one-sided p-value is less than 5% then the null hypothesis of no treatment effect is rejected. If the one-sided p-value is additionally less than 2.5%, then the serlopitant-based regimen will have met the generally accepted level of evidence required to demonstrate efficacy.

The target sample size of 200 randomized and dosed subjects (100 per group) has been determined based upon a 1:1 allocation of subjects to treatment groups and a 5% one-sided alpha level. A sample size of 200 subjects results in at least 90% power assuming a placebo 4-point responder rate of ███% and serlopitant 4-point responder rate of ███% at Week 10.

The sample size calculations have been performed in PASS 13 (“PASS 13 Power Analysis and Sample Size Software” 2014) and used a Chi-Squared test. The primary analysis will control for the stratification factors. It is expected that this unstratified power estimate will under-estimate the true power as it does not take the variance reduction resulting from stratification into account ([Matts and Lachin 1988](#)).

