2.7 Handling of Missing Data

Summary statistics will generally be reported based upon observed data. Should a determination of treatment period (on treatment or pre-treatment) be required for adverse events or concomitant medication but the corresponding date is missing or partial, the event/medication will be considered on treatment unless the portions of the date that are available indicate this is not possible.

If a subject fails to complete their eDiary for a week or more, the WI-NRS endpoints, including the primary endpoint, may be missing. In this case, the WI-NRS change from baseline value will be imputed. The approach uses the subject's last week with data. From that point forward their trajectory will be imputed based upon the trajectory of their treatment group.

The imputation approach first determines the average change between analysis weeks (see [Table 4](#)) for each treatment group. The change between analysis weeks is the difference between results at adjacent analysis Weeks (e.g. results at Week 10 – results at Week 8). Any missing change from baseline results will be imputed by combining the last known value and the treatment group mean weekly differences from that point forward. CCI

This imputation algorithm is only used if the intercurrent events (see [Section 2.6](#)) did not occur.

For the responder endpoints, the same imputation will be performed and the responder status determined based upon the change from baseline.

Missing data imputation will only be used for the WI-NRS endpoints.

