2.8 Sensitivity Analyses, Subgroups and Covariates

Descriptive statistics for the WI-NRS responder rate at Week 10 will be provided for the subgroups indicated below. Forest plots of the difference and confidence interval for this difference will also be created. The subgroups include,

- Sex
- Age Group
 - (≤ 64 years, > 64 years)
 - (< 50 years, ≥ 50 years).
- Race - all race groups with less than 30 subjects will be combined with 'Other'

- Baseline WI-NRS (< 8.5, >= 8.5)
- Duration of chronic pruritus (< 1 yr, 1-5yrs,>5 yrs)

Additionally, the WI-NRS responder rates at Week 10 will be summarized for subject with and without the following post baseline events. These are post-baseline factors and may be correlated with treatment outcomes.

- Study Disposition
 - Completed study
 - Did not complete the study
- Ever require / did not require rescue therapy for treatment of worsening pruritus
- Treatment completion (completed treatment, did not complete treatment).

To investigate the impact of missing data, missing WI-NRS data will be derived using the method of Markov Chain Monte Carlo (MCMC) multiple imputation. Imputation will be conducted within each treatment group independently, so the pattern of missing observations in one treatment group cannot influence missing value estimations in another. The MCMC imputation will use the observed results at each timepoint. For each imputation process, 1000 imputations will be performed. To mimic the original missing data algorithm, the continuous values will be imputed and the responder status will be determined. The intercurrent events rules (see [Section 2.6](#)) will continue to be used. A CMH test, identical to the test used for the primary endpoint, will be used based upon the imputed responder status.

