2.9 Safety Analyses

Safety endpoints will be summarized with descriptive statistics. All safety summaries and analyses will be performed using the safety population. Vital signs, laboratory, and ECG results will be summarized by timepoint and treatment. Adverse events and concomitant medications/procedures will be summarized overall.

Prior and concomitant medications and procedures will be coded by the World Health Organization (WHO) Drug Dictionary version 2018/Q3. Medications and procedures will be considered concomitant unless they ended prior to treatment.

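### The adverse-event and concomitant-medication tables pool treatment with a 5-week follow-up in which antipruritics become permitted; add tables split by period and date-limit the rescue split

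*SAP*

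**What the plan says.** **Event definition and summary.** SAP 2.3.7.1: "An AE is considered treatment emergent, TEAE, if it began on the day of first treatment or after". The definition has a start and no end, and the same section records AEs to the end of follow-up. SAP 2.9: "Adverse events and concomitant medications/procedures will be summarized overall". SAP 3.3.3 treats any medication with a start or stop date on or after first dosing as concomitant, again without an end. The AE tables in SAP 3.5.1 have no split by period.

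**Period categories.** The rule for missing or partial dates in Protocol 8.2 opens with three periods: "Should a determination of treatment period (on treatment, pre-treatment, follow-up) be required for adverse events". The matching sentence in SAP 2.7 has two: "Should a determination of treatment period (on treatment or pre-treatment) be required for adverse".

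**Background treatment.** Protocol 5.7.2 excludes topical and systemic antipruritics, including H1 antihistamines, doxepin, gabapentin and pregabalin, up to the end of treatment. It then says: "Use is discouraged, though permitted, in the follow-up period". Its other list of excluded therapies stays in force through follow-up.

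**Rescue.** SAP 2.8 tabulates Week 10 response by "Ever require / did not require rescue therapy for treatment of worsening pruritus", with no date limit.

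**The concern.** Safety and tolerability is the secondary objective. The overall tables cover two stretches of time with different exposure and different rules on background therapy. An event that starts on study drug with antipruritics barred is counted with one that starts four weeks after the last dose, possibly under a newly started antipruritic. A reader of the table cannot tell them apart. Likewise, the medication table cannot separate antipruritics used on treatment from those started in follow-up.

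The SAP is also uneven. It reports visit-based measures, including the Epworth Sleepiness Scale (ESS), with Follow-up as its own time point, but not AEs or medications. Protocol 7.2.3 records the highest severity grade within a study period, whereas SAP 3.5.1 takes the worst grade over the whole study.

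The rescue split raises a related timing problem. SAP 2.6 identifies rescue from a site indication that a medication was taken for worsening pruritus. If a site gives that indication for a therapy begun in follow-up, a Week 10 response is sorted by something that happened after the outcome was measured.

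**Working it through.** **The plan's own figures.** The documents give no AE rates by period, so there is nothing of that kind to reproduce. The design figure (200 subjects, at least 90% power, one-sided 5%) concerns the primary test. Its responder rates are blacked out, and this point does not depend on it. With 100 subjects per arm, one subject is one percentage point.

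**Share of the window after the last dose.**
- Completer: 10 weeks of dosing plus 5 of follow-up gives 35/(70 + 35) = 33%.
- Subject who stops at Week 2 and has the 5-week follow-up of Protocol 5.6: 35/(14 + 35) = 71%.

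**Remaining exposure.** Protocol 1.3.1 gives a half-life of 45 to 86 hours. Five half-lives are 5 × 45/24 = 9.4 days to 5 × 86/24 = 17.9 days, or 27% to 51% of the 35 days. At the long end, (35 − 17.9)/105 = 16% of the window lies beyond five half-lives.

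**Effect of pooling.** Let p be the on-treatment risk and q the follow-up risk in an arm. If the periods are independent and each subject is counted once, the pooled risk is 1 − (1 − p)(1 − q). With equal q in both arms the risk difference becomes (p_S − p_P)(1 − q), which barely moves for small q, while the risk ratio moves towards 1.

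*Fatigue.* Protocol 1.3.3 reports 9.4% on serlopitant and 6.3% on placebo in TCP-102. Treating these as on-treatment rates is an assumption, and every q is assumed. Differences and ratios are computed before rounding.

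| Follow-up risk, serlopitant / placebo | Pooled serlopitant | Pooled placebo | Difference (points) | Ratio |
|---|---|---|---|---|
| none | 9.4% | 6.3% | 3.1 | 1.49 |
| 5% / 5% | 13.9% | 11.0% | 2.9 | 1.27 |
| 2% / 4% | 11.2% | 10.0% | 1.2 | 1.12 |
| 4% / 2% | 13.0% | 8.2% | 4.9 | 1.59 |

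For the third row: 1 − 0.906 × 0.98 = 0.112 and 1 − 0.937 × 0.96 = 0.100. The fourth row shows that the opposite imbalance widens the difference.

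*Somnolence.* TCP-101 reports 4.7% at 5 mg and no placebo figure. With an assumed placebo rate of 1.6%, the difference is 3.1 points and the ratio 2.94.
- Equal follow-up risk of 2%, 5% or 10%: difference 3.0, 2.9 or 2.8 points; ratio 1.85, 1.45 or 1.24.
- 2% on serlopitant and 5% on placebo: 6.6% against 6.5%, ratio 1.01.
- 5% and 10%: 9.5% against 11.4%, so the sign reverses.
- Over assumed placebo rates of 1% to 3%, an equal 5% takes the ratio from 4.70 to 1.59 at one end and from 1.57 to 1.21 at the other.

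**The case against.** A reader might infer that the SAP has removed a period-specific safety analysis promised in the protocol. The documents do not support that. The protocol's three-period wording sits in the missing-date rule. Protocol 5.7 and 7.2.1 run concomitant therapy and AE recording through follow-up, and Protocol 8.9.1 plans no split by period. Since the SAP's definitions have only a start boundary, two categories are enough for its date rule. This objection stands in full.

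A reader might also infer that pooling hides sedative-type effects. That would need the permitted antipruritics to cause such events and to be used more on placebo. The documents say neither. Protocol 1.1 mentions only general trade-offs in tolerability and safety, and use in follow-up is discouraged. Nor are the five weeks simply off drug, given the half-life.

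Existing protection is real but partial. The ESS is reported by time point, but it is exploratory and measures sleepiness only. Treatment-related events and events leading to discontinuation have their own tables, but relatedness is an investigator's judgement. AEs and medications are listed by subject, and on-treatment use of an excluded therapy is recorded as a deviation, but a listing is not a comparison between arms.

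On rescue, the protocol synopsis defines it as an excluded therapy for worsening pruritus, so a permitted follow-up antipruritic arguably does not qualify. The table is also descriptive, and SAP 2.8 already warns that these factors may correlate with outcome. That warning does not cover rescue begun after Week 10.

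Finally, counting every event after first dose is inclusive and keeps late and withdrawal events in view. That is a good reason to keep the overall table as the main one.

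**Conclusion.** The point holds as a gap in reporting. The overall tables combine two background-treatment regimes, with a third of a completer's window after the last dose. Ratio dilution occurs even with equal follow-up rates (1.49 to 1.27 in the fatigue illustration at 5%), while the difference then hardly changes (3.1 to 2.9 points). A materially smaller or reversed difference requires more follow-up events on placebo, which is an assumption, and the opposite pattern would enlarge it. No masking is established. The defect is that the planned summary tables could not show which of these happened.

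The sizes rest on independent periods, on prior-study rates taken as on-treatment rates, and on assumed follow-up rates. No safety test is planned, and the primary analysis is unaffected. This is a cheap improvement to the SAP.

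**What to change.** 1. **SAP 2.7:** restore follow-up as a third category, as in Protocol 8.2, and keep the default that an undated event counts as on treatment unless the known part of the date rules it out.
2. **SAP 2.9, 3.3.3 and 3.5.1:** keep the overall treatment-emergent AE and concomitant-medication tables as the main ones. Add supplementary versions split by onset or start date into the treatment period (first to last dose) and follow-up. Optionally divide follow-up at a pre-specified lag, such as 18 days (five half-lives at 86 hours). The lag should not define the main table: last dose plus 18 days would still take in 18/35 = 51% of the period in which antipruritics are permitted, and would move later events out of the main table.
3. **SAP 2.8:** classify Week 10 response by rescue started on or before Day 70, the last day of the Week 10 diary window in SAP Table 4, in place of rescue at any time.

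The cost is SAP wording, a few extra tables and a cut-off fixed before unblinding. The dates are already collected, so nothing changes for sites or subjects.
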